### 1.5 Correlative Studies

N/A

## 2.0 STUDY OBJECTIVES

### 2.1 Primary Objectives

2.1.1 To obtain an estimate of the efficacy of the e-Motivación app for improving screening colonoscopy uptake among Latinos  
[For details, please see section 5.2.2; a detailed flowchart of the App is attached – please see Appendix B]

### 2.2 Secondary Objectives

N/A

### 2.3 Exploratory Objectives

N/A

### 2.4 Endpoints

2.4.1 Screening colonoscopy completion status in medical charts six months after participants complete the consent for the study will be used as a proxy for efficacy of the e-Motivación app in improving screening colonoscopy uptake among Latinos. In our previous study with a similar sample, less than 10 of 900+ participants reported completing the colonoscopy at a different hospital. As such, for the proposed project, if the medical chart does not report that a colonoscopy was completed, the colonoscopy will be documented as "not completed".

## 3.0 PATIENT ELIGIBILITY

Eligibility waivers are not permitted. Subjects must meet all of the inclusion and exclusion criteria to be registered to the study. Study treatment may not begin until a subject is registered.

**3.1 Inclusion Criteria**

- 3.1.1 Self-identified as Latino,a,x
- 3.1.2 English or Spanish-speaking
- 3.1.3 Received a physician referral for a screening colonoscopy
- 3.1.4 Has access to a tablet, smartphone, or computer with working Internet

**3.2 Exclusion Criteria**

- 3.2.1 Hearing or vision impaired
- 3.2.2 Aim 1 or 2 participant

**4.0 TREATMENT PLAN****4.1 Administration**

Participants will be randomly assigned to one of two groups: e-Motivación (N=40) or control group (N=40). Participants assigned to the e-Motivación condition will complete the e-Motivación app on a personal device of their choice (for details, please see section 5.2.2; a detailed flowchart of the App is attached – please see Appendix B). Participants assigned to the control group will watch a general health video on a personal device of their choice.

**4.2 Toxicities and Dosing Delays/Dose Modifications**

N/A

**4.3 Concomitant Medications/Treatments**

N/A

**4.4 Other Modalities or Procedures**

N/A

**4.5 Duration of Therapy**

N/A

**4.6 Duration of Follow Up**

Six months following the consent to take part into the study, medical charts will be reviewed to determine colonoscopy completion status.

**4.7 Removal of Patients from Protocol Therapy**

Patients can be taken off the study at any time at their own request, or they may be withdrawn at the discretion of the investigator for safety, behavioral or administrative reasons. The reason(s) for discontinuation will be documented and may include:

- 4.7.1 Patient voluntarily withdraws from the study (follow-up permitted);
- 4.7.2 Patient withdraws consent (termination of treatment and follow-up);
- 4.7.3 Patient is unable to comply with protocol requirements;

---

4.7.4 Continuation on the study would not be in the patient's best interest based on the judgement of the treating physician, study PI, study doctor, sponsor or study institutions

**4.8 Patient Replacement**

N/A

**5.0 STUDY PROCEDURES**

**5.1 Screening/Baseline Procedures**

A HIPAA waiver will be requested to access patient lists and medical records to screen for study eligibility. Patients' lists (i.e. CERNER, Pool of Direct Access for Colonoscopies referrals, MSHS EPIC screening colonoscopy lists) and medical records will be obtained to identify and screen for potential participants. A member of the research team will inform members of the healthcare team (e.g., patient navigators, schedulers, physicians, medical assistants) which patients may be eligible for the study.

Members of the healthcare team, including patient navigators and primary care providers, will introduce the study to eligible patients (e.g., identify as Latino, received a primary care referral for a screening colonoscopy). If patients are interested in learning more about the study, and agree to be contacted, the member of the healthcare team will provide the research staff with the patient's contact information. If patients are being recruited in person, the member of the healthcare team will introduce the patient to the member of the research team, in person, after an in-clinic appointment.

The research staff will then contact (via email/over the phone/in person) the eligible patient to provide the patient with more details about the study. If the patient is interested in participating in the study and meets eligibility criteria, the patient will complete the consent form on RedCAP (emailed/texted/shown on the device of the person obtaining consent).

The screening procedures include:

**5.1.1 *Obtaining Informed Consent***

**5.1.2 *Reviewing Subject Eligibility Criteria***

**5.1.3 *Collecting Demographics***

[Age;; Length of permanence in the US; Ethnicity; Race; Preferred language; Territory of identity; Gender; Highest level of education; Marital Status; Estimated total income for the household for the past year]

**5.1.4 *Collecting Medical History***

[Referral for a screening colonoscopy (Yes/No); Previous experience of colonoscopy before (Yes/No) - If yes: year of last colonoscopy; Diagnosis of colorectal cancer (Yes/No); Diagnosis of a gastrointestinal disease (Yes/No); Family history of colorectal cancer (Yes/No) - If yes: Mother, Father, Brother, Sister, Child, Other; PRIMARY type of health insurance]

**5.2 Procedures During Treatment**

Consented participants will first complete a demographics questionnaire administered over the phone or in-person. Then, the participant will be randomly assigned to either the intervention condition (e-motivacion) or the control condition (general health video). The

participants will be emailed or texted a hyperlink. The hyperlink will either direct the participants to the app or to a general health video (see Appendices A and B, for details).

#### 5.2.1 *Completing an interviewer-administered baseline questionnaire*

[Age; Length of permanence in the US; Ethnicity; Race; Preferred language; Territory of identity; Referral for a screening colonoscopy (Yes/No); Previous experience of colonoscopy before (Yes/No) - If yes: year of last colonoscopy; Diagnosis of colorectal cancer (Yes/No); Diagnosis of a gastrointestinal disease (Yes/No); Family history of colorectal cancer (Yes/No) - If yes: Mother, Father, Brother, Sister, Child, Other; Gender; Highest level of education; PRIMARY type of health insurance; Marital Status; Estimated total income for the household for the past year, before taxes]

#### 5.2.2 *Interacting with the App (condition group)*

The app is designed to be used in English or Spanish, based on participant preference. The content of the app is drawn from our preliminary studies and the current MI literature, with particular emphasis on the most recently published MI guidelines (MI-III). The e-Motivación app is designed to be user-friendly and to require low computer literacy. Consistent with the published MI guidelines, the e-Motivación app involves four sequential phases: **(1) Engaging:** During the *engaging phase*, participants will watch a video welcoming them to the intervention. Drawing from other e-MI interventions, a live video coach will be used. **(2) Focusing:** During the *focusing phase*, participants will reaffirm their willingness to discuss the decision to have a screening colonoscopy. Then, using the “elicit-provide-elicit” MI technique, through touch screen multiple-choice questions, participants’ knowledge about CRC prevention will be assessed. If participants lack knowledge regarding certain aspects of the colonoscopy or CRC in general, they will be given the option to view information videos (e.g., how to prepare for a screening colonoscopy). **(3) Evoking:** During the *evoking phase* of the intervention, participants will rate their perceived importance of having a colonoscopy and their level of confidence in their ability to complete the procedure. Based on their responses, participants will complete interactive MI exercises (e.g., decisional balance, values clarification) to help improve their perceived importance and confidence. **(4) Planning:** During the *planning phase* of the intervention, participants will be offered the option to watch a video designed to orient them to complete an action plan (e.g., scheduling the colonoscopy, planning for an escort).

[A detailed flowchart of the App is attached – please see Appendix B]

#### 5.2.3 *The study team will have access to back end information that will allow authorized members to know which parts of the App were utilized by the user and how. That information will be linked to each participant by the ID that users are required to enter to log into the app. Watching a General Health Information Video (control group)*

For the control group, the investigators will not be able to know if the video was watched by the participant or not.

### 5.3 Follow-up Procedures

#### 5.3.1 *Reviewing Medical Charts to Determine Colonoscopy Completion Status and relevant medical information [Screening colonoscopy referral and scheduling date; Screening colonoscopy completion (yes/no); Screening colonoscopy completion date; bowel prep quality; number of cancellations and no-shows;*

***Received patient navigation/care coordination(yes/no); reasons for not completion (if applicable)]***

6 months following consent to participate in the study

**5.4 Time and Events Table**

Research Timeline [Aim III]	Months 1-3	Months 4-6	Months 7-9	Months 10-12	Months 13-15
Recruitment	X	X	X		
Informed Consent	X	X	X		
Baseline data (demographics & medical history)	X	X	X		
Review of medical charts (colonoscopy completion status)			X	X	X
Analyze pilot study data					X
Disseminate results					X

**5.5 Removal of Subjects from Study**

Patients can be taken off the study at any time at their own request, or they may be withdrawn at the discretion of the investigator for safety, behavioral or administrative reasons. The reasons for discontinuation will be documented and may include:

- 5.5.1 Patient voluntarily withdraws from the study (follow-up permitted);
- 5.5.2 Patient withdraws consent (termination of treatment and follow-up);
- 5.5.3 Patient is unable to comply with protocol requirements;
- 5.5.4 Continuation on the study would not be in the patient's best interest based on the judgement of the treating physician, study PI, study doctor, sponsor or study institution

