**6.0 Measurement of Effect**

Screening colonoscopy completion status (in medical charts) six months after the patient expressed informed consent to participate in the study will be the proxy for efficacy of the e-Motivación app in improving screening colonoscopy uptake among Latinos. If the medical chart does not report that a colonoscopy was completed, the colonoscopy will be documented as "not completed". This decision is informed by a study that we have conducted with a similar sample, where less than 10 out of 900+ participants reported completing the colonoscopy at a different hospital.

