## 10.3 Data Analyses Plans

*Analyses of covariates:* Due to the use of randomization, significant baseline differences (e.g., gender, age) between condition and control groups are not expected. However, contingency tables and t-tests will be performed to determine any differences between the two arms. Using a  $p$  value of  $\leq 0.15$ , any consistent pattern of correlation for any of the covariates would suggest their inclusion in the primary data analysis model.

*Effect size estimate:* Logistic regression analyses will be used to evaluate an estimate of the efficacy. The model will include any covariates that differentiate the intervention and control groups. The effect size of the treatment group will be used as an indicator to inform power calculations for a future RCT. The power calculations will inform the appropriate sample size needed for the RCT.

*Missing data:* The e-Motivación app is a one-time intervention and the questionnaire to assess demographics and medical history of participants will be conducted as an interview. Therefore, we anticipate minimal missing data.

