4. *Indicate the frequency at which ACCUMULATED safety and data information (items listed in number 3 above and interim analysis of efficacy outcomes) will be reviewed by the monitor(s) or the Data Monitoring Committee (DMC). Although this information must be reviewed at least annually, the higher the study risks, the more frequently reviews must be scheduled.*

The PI will monitor the progress of the trial and the safety of participants on an ongoing basis. The procedures of this study, such as regular meetings with research staff and the entire study team, will ensure prompt discussion and reporting of all study conduct issues, including adverse events. During these meetings, the PI will focus on participant safety by reviewing adverse events, study progress (e.g. recruitment, retention, protocol adherence), data integrity and study outcomes. Additionally, we anticipate that risk-benefit ratio will remain favorable throughout the study. However, if at any point it is not, we will stop the study and re-evaluate study procedures in order to ensure a positive risk-benefit ratio for participants.

The table below describes each data monitoring activity, responsible staff person, and frequency of review. Tracking forms will be developed to document the occurrence of all reviews. The PI will review all reports as they are generated.

Activity	Report	Timing of review
Informed Consent	Quality control of each new consent by Research Coordinators	PI reviews all consents upon receipt
Protocol Adherence (both Subjects and Research Staff)	Weekly report generated by Research Coordinators	Weekly PI review

Adverse Events	Weekly report generated by Research Coordinators	Weekly PI review
Study Retention	Weekly report generated by Research Coordinators	Weekly PI review
Review of Medical Charts to Assess Colonoscopy Completion Status	Weekly report generated by Research Coordinators	Weekly PI review
Self-Report Information	PI and other study staff will review all self-report materials and complete fidelity checklist	PI will review data weekly for completeness and accurate entry into a database for analysis

5. *Where applicable, describe rules which will guide interruption or alteration of the study design.*

N/A

6. *Where applicable, indicate dose selection procedures that will be used to minimize toxicity.*

N/A

7. *List any specialized grading system that will be used to evaluate adverse events (e.g., National Cancer Institute Common Toxicity Criteria).*

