The severity of an adverse event is graded as follows:

- Mild (grade 1): the event causes discomfort without disruption of normal daily activities.
- Moderate (grade 2): the event causes discomfort that affects normal daily activities.
- Severe (grade 3): the event makes the patient unable to perform normal daily activities or significantly affects his/her clinical status.
- Life-threatening (grade 4): the patient was at risk of death at the time of the event.
- Fatal (grade 5): the event caused death.

8. *Describe procedures that will be used to assure data accuracy and completeness.*

Study data will be entered by a Research Coordinator trained to enter data into a password-protected, secure database on REDCap. To ensure the validity and integrity of study data, the PI will oversee all data management responsibilities. Data entry, level of accuracy and percentage of error in data entry will be discussed with the study team on a regular basis. Monthly meetings (either in person or via video/telephone conference) will be held with the entire study team.

Thorough training of Research Coordinators is also designed to ensure adequate protection of human subjects. All Research Coordinators will receive all required training and certification in Mount Sinai's human subjects in research. Research Coordinators will be required to participate in a training program designed to ensure that they administer the interviews and evaluate participant responses in a sensitive manner. Research Coordinators will be trained to speak clearly and audibly and let participants determine the pace of the interview.

Protocol compliance will be monitored at the weekly research staff meetings. The PI will meet with the study staff on a weekly basis to train and ensure adherence to the intended protocol. The PI will be responsible for updating all investigators regarding any study related issues that arise of that need to be addressed.

The medical chart abstraction will be conducted by a research team member. A second research team member will review 20% of the medical charts to confirm accuracy.

9. *Should a temporary or permanent suspension of your study occur, in addition to the PPHS, to whom (NIH, FDA, sponsor, IRB) will you report the occurrence?*

IRB and Program Officer of the National Institute On Aging/NIH/DHHS

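### Could removing app non-users bias the app's odds ratio, given that section 10.3 names no analysis population?

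*Combined protocol and SAP*

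**What the plan says.** Sections 4.7 (removal from protocol therapy) and 5.5 (removal from study) carry almost the same list. Withdrawal may be at the investigator's discretion, and one listed reason is "Patient is unable to comply with protocol requirements". That phrase is not defined. In 5.5, voluntary withdrawal (5.5.1) allows follow-up and withdrawal of consent (5.5.2) ends it. Items 5.5.3 (inability to comply) and 5.5.4 (the patient's best interest) do not mention follow-up.

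Under 5.2.3, back-end data let the team "know which parts of the App were utilized by the user and how", linked to the participant's ID. For the control arm, "the investigators will not be able to know if the video was watched by the participant or not". The monitoring table in 11.5.1 item 4 gives the principal investigator weekly reports on subject adherence and on "Review of Medical Charts to Assess Colonoscopy Completion Status".

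The endpoint is colonoscopy completion in the chart six months after consent (2.4.1, 4.6, 6.0, 10.1). Section 6.0 also covers the chart with no record: "If the medical chart does not report that a colonoscopy was completed", the outcome is entered as not completed. Section 10.2 sets 40 participants per arm, and 4.8 (replacement) is not applicable. Section 10.3 specifies logistic regression, names no analysis population and says of the result: "The effect size of the treatment group will be used as an indicator to inform power calculations for a future RCT".

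**The concern.** Three features together look unsafe. Removal is discretionary, non-use can be seen in one arm only, and no sentence says that removed participants stay in the analysis. Someone who never opens the app could be classed as unable to comply and withdrawn, while a control participant who never plays the video could not be identified. Exclusions would then fall on one arm and depend on behaviour after randomisation.

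If those excluded complete colonoscopy less often than the rest, the app looks better than it is. The estimate feeds the sample size of the next trial, so an inflated odds ratio would make that trial too small. The principal investigator also sees adherence and outcome reports in the same week, so a removal could be decided with the outcome in view.

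A lesser worry is that chart abstraction is not stated to be masked to arm.

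**Working it through.** **Step 1. What would have to happen.** The bias needs four links, all of them true:

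1. Not using the app is treated as inability to comply. The documents do not say this.
2. The investigator then withdraws the participant. This is permitted but not required. The app is a one-time intervention (10.3), so little treatment remains to withdraw from once the link has been sent.
3. Withdrawal stops chart review or removes the participant from the model. The documents do not say this.
4. Non-users complete at a different rate from users. The documents give no figure.

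**Step 2. What the text says about link 3.**

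- 4.6 and 10.1 place chart review six months after consent, with no condition on using the app or video.
- 2.4.1 and 6.0 give an outcome for every chart reviewed, because a chart with no record counts as not completed.
- In 5.5, consent withdrawal is the only reason said to end follow-up. Voluntary withdrawal, a firmer exit than not opening an app, allows it.
- 10.2 counts 40 and 40, and 10.3 describes no exclusion or per-protocol set.

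Together these give every randomised participant an outcome in the assigned arm, apart from those who withdraw consent.

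**Step 3. Size if link 3 were nevertheless to hold.** From the documents: 40 per arm (10.2). Assumed, because the documents give no rates: completion p = 50% in both arms (true odds ratio 1.00), k app non-users left out, a share r of them completing, and no one left out of the control arm.

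App-arm rate after removal: p_a = (40p − k·r)/(40 − k). Odds ratio: OR = [p_a/(1 − p_a)] / [p/(1 − p)]. At p = 50% the denominator is 1.

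| Left out (k) | r = 0% | r = 25% | r = 50% | r = 80% |
|---|---|---|---|---|
| 0 | 20/20 = 1.00 | 1.00 | 1.00 | 1.00 |
| 4 | 20/16 = 1.25 | 19/17 = 1.12 | 18/18 = 1.00 | 16.8/19.2 = 0.88 |
| 8 | 20/12 = 1.67 | 18/14 = 1.29 | 16/16 = 1.00 | 13.6/18.4 = 0.74 |

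For k = 8, r = 25% gives 1.17 at p = 40% and 1.47 at p = 60%; r = 80% gives 0.64 and 0.81. The sign of the bias depends on r alone. Lower completion among non-users is plausible. So is the reverse: everyone enrolled already has a referral (3.1.3) and recruitment runs partly through navigators (5.1), so some may skip the app because the procedure is already being arranged.

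**Step 4. Effect on the next trial.** Take the odds ratio of 1.6 cited in section 1.1 as the truth, with control completion 50%. The app rate is 1.6/2.6 = 61.5%, or 24.6 of 40. The two-proportion formula (pooled variance under the null, 80% power, two-sided 5%) gives 290 per arm. Now leave out 4 app participants:

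- r = 25%: 23.6/36 = 65.6%, OR = 23.6/12.4 = 1.91, and 157 per arm.
- r = 80%: 21.4/36 = 59.5%, OR = 21.4/14.6 = 1.47, and 431 per arm.

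The next trial could come out too small or too large.

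**Step 5. Against sampling error.** With 20/40 in each arm, SE(log OR) = √(4/20) = 0.447 and exp(1.96 × 0.447) = 2.40. The 95% limits are a factor of 2.4 either side, wider than any entry in the Step 3 table.

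**The case for a change.** The best case for a change is that the safeguard is inferred. The rule for a chart with no record says how to code an outcome; it does not say that a withdrawn participant's chart will be opened. Section 5.5 states follow-up status for two reasons and omits it for two, so staff could read the omission either way. The choice could be made after app use, and possibly the outcome, has been seen. A wide confidence interval does not reveal selective exclusion, and one sentence would settle the matter at no cost.

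Much of this stands as description. The analysis population is unstated, the visibility of task use differs by arm, and the figures in Step 4 would matter if people were left out. What does not stand is the move from silence to bias. The plan's default is chart review for everyone who consented, and leaving someone out would mean departing from it. Analysing a randomised binary outcome by assigned arm is what an analyst would do unprompted. A departure would also leave traces, since 5.5 requires reasons for discontinuation to be documented and 11.5.1 monitors drop-outs and requires a weekly retention report.

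On masking, the endpoint is a yes/no chart entry, and 11.5.1 item 8 provides a check: "A second research team member will review 20% of the medical charts to confirm accuracy". That section assigns abstraction to a research team member, who need not be whoever prepares the adherence reports. Nothing in the documents shows a gain from masking.

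**Conclusion.** No change to the plan is called for. The gap is missing detail that the surrounding text fills in one direction: all 80 participants are analysed as randomised with the six-month chart outcome, apart from any who withdraw consent. Under that reading the expected odds ratio with no true effect is 1.00 whatever the pattern of app use.

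The hypothetical bias is not negligible. With 8 of 40 app participants left out, it runs from 1.29 down to 0.74 as completion among them goes from 25% to 80%. But it needs a chain of steps the plan does not prescribe, and its direction cannot be established from the documents. These sizes rest on assumed completion of 50% and assumed numbers left out.

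The conclusion rests on reading 4.6, 6.0 and 10.1 as applying to everyone who consented, which is their plain sense. A report that excluded participants for not using the app would be a departure from the plan and should be judged as one.
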